2.7.1 INITIAL SKIN ASSESSMENT

At the baseline visit on day 0, a skin assessment is performed to check and document the initial condition of the skin in the study area. It will be documented whether an IAD (classified according to GLOBIAD [25]) is already present and if the skin is intact or eroded (according to *Proceedings of the Global IAD Expert Panel* [35]). Other dermatological conditions in the study area will also be documented.

Study participation with pre-existing IAD is only possible if it is a mild form with early signs of IAD and intact skin (GLOBIAD category 1 A). If the initial skin assessment reveals a moderate or severe form (including skin loss or clinical sign of infection) of IAD (GLOBIAD category 1 B; 2 A or 2 B), the participant will be excluded. Other dermatological conditions or skin affections (at investigational areas of the skin) requiring dermatological treatment or interfering with the conduct of the study also lead to exclusion.

2.7.2 MEXAMETER MEASUREMENT

The erythema level will be measured with a modular system consisting of the *Mexameter® MX 18* probe, connected to the basic device *Multi Display Device (MDD) 4* (Courage + Khazaka, Cologne, Germany). The probe measures the haemoglobin (erythema) components of the skin, which are mainly responsible for its color. The measuring principle is based on absorption and reflection. For the measurement, the probe emits light with three specific wavelengths and a receiver unit measures the reflected light from the skin. As the quantity of emitted light is standardized, it is possible to calculate the quantity of light absorbed, by measuring the light reflected by the skin. Values are displayed in device-specific arbitrary units (AU) and range from 0 AU to 999 AU, whereby higher readings indicate more extreme erythema.

2.7.3 RESIDENT/PATIENT REPORTED OUTCOME MEASURES

Participants are asked if IAD related itch is present or not. IAD related pain will be assessed with a numeric rating scale (NRS) from 0 (= no pain) to 10 (= worst possible pain) (**Fehler! Verweisquelle konnte nicht gefunden werden.**) for patients/residents without cognitive impairment (according to Mini-Mental-State-Examination (MMSE) [29] (**Fehler! Verweisquelle konnte nicht gefunden werden.**) with scores of 24 or higher). For patients/residents with dementia (according to MMSE [29] scores of < 24) the Pain Assessment in Advanced Dementia (PAINAD-G) [30, 31] scale will be used (**Fehler! Verweisquelle konnte nicht gefunden werden.**). Patient satisfaction is assessed by

NRS from 0 (= dissatisfied) to 10 (= very satisfied) (**Fehler! Verweisquelle konnte nicht gefunden werden.**) for patients/residents with MMSE [29] scores of 24 or higher. Definition according to [32].

2.7.4 PARTICIPANTS TIMELINE

In total, eight study visits are planned. After inclusion, residents will be followed-up for 14 days. Written informed consent will be obtained prior study participation by the residents/patients themselves or their legal representatives, if applicable. Demographic information (e. g. age, sex, care level), incontinence type according to medical records, medical information (e. g. relevant main medical diagnoses and relevant regular medication) and further care specific data is collected for all participants. A detailed list of variables and how they will be collected (e. g. device/instrument/scale and metric as well as measurement time points) is shown in Table 4. The planned trial flow is shown in Figure 1 and a schematic overview of the detailed study schedule for the individual participants is shown in Table 3.

[figure not shown]

Figure 1: Overview of the planned trial flow.

Table 3: Study schedule for individual participants.

	Days																
	Enrollment	Allocation	Post-allocation														Close-out
Timepoint	-5 to 0	0	1	2	3	4	5	6	7	8	9	10	11	12	13	14	
Formal requirements and allocation																	
Eligibility screening	x																
Informed consent	x																
Randomization and allocation		x															
Participant characteristics																	
Demographic variables (e.g. age, sex, care level)		x															
Relevant medical diseases		x															
Relevant medications		x															
Physical function (Barthel-Index)		x															
Cognitive status (MMSE)		x															
Incontinence characteristics		x															
Clinical skin assessment																	
Gent Global IAD categorization (GLOBIAD)		x		x		x		x		x		x		x		x	
Erythema (visual inspection)		x		x		x		x		x		x		x		x	
Erythema (instrumental measurement)		x		x		x		x		x		x		x		x	
Erosion		x		x		x		x		x		x		x		x	
Maceration		x		x		x		x		x		x		x		x	
IAD-related pain (NRS or PAINAD-G)		x		x		x		x		x		x		x		x	
IAD-related itch		x		x		x		x		x		x		x		x	
Patient satisfaction (NRS)		x		x		x		x		x		x		x		x	
(Serious) Adverse Events or Incidents		x		x		x		x		x		x		x		x	
Interventions and study-related procedures																	
Study arm 1: Conduction of the standardized skin cleansing regime and application of the film-forming skin protectant			●	—	—	—	—	—	—	—	—	—	—	—	—	—	●
Study arm 2: Conduction of the standardized skin cleansing regime and application of the hydrophobic skin protectant			●	—	—	—	—	—	—	—	—	—	—	—	—	—	●
Study arm 3: Conduction of the standardized skin cleansing regime, no additional skin protectant			●	—	—	—	—	—	—	—	—	—	—	—	—	—	●
Other																	
Skin care diary completed by nurses			●	—	—	—	—	—	—	—	—	—	—	—	—	—	●

2.8 SAMPLE SIZE

2.8.1 WHOLE TRIAL

Due to the exploratory nature of the trial, a formal sample size calculation is not applicable [23]. The trial has two strata (I) sex (male/female); (II) condition of the skin (no IAD vs. IAD Category I) and three study arms. Based on these conditions and following the recommendations for exploratory trials [36], a sample size of $n = 60$ participants per group is considered feasible and sufficient to describe group differences. In order to compensate a possible loss-to-follow-up, $n = 70$ patients per group will be included.

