3. METHODS: ASSIGNMENT OF INTERVENTIONS

3.1 SEQUENCE GENERATION

A computer-generated, block-randomization with 1:1:1 allocation ratio per trial arm will be used. In order to detect any possible sex-related differences or interactions [37] the randomization will be stratified according to males and females. Two independent randomization lists are generated according to the same principle, one for participants in the geriatric hospitals/wards and one for the participants of the nursing homes. This is done to ensure that there is an equal distribution of allocation in both settings. Computerized random numbers will be generated by the statistician not involved in study planning or any further study-related procedures or the associated data analysis. The random number list is kept with the statistician until the end of the study.

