1.2 Trial design

The trial is designed as a randomized controlled (ratio 1:1:1), parallel group, three-arm, assessor-blinded exploratory trial. Patients are randomized stratified by sex (male/female) into the treatment arms. The study was conducted in geriatric hospitals/geriatric wards of participating hospitals and in institutional long-term care facilities of the federal state of Berlin, Germany.

2 Analysis sets

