5.1 Missing values

In all analyses, missing values on either the outcome measures or on the covariates will be handled by using multiple imputation by chained equation (MICE) with $m = 30$ imputed datasets if MAR or MCAR assumption holds. To evaluate whether individual missings are MAR, MCAR or MNAR we will use information on reasons of missings or drop out (e.g. if patients drop out due to worsening of health status or not). In case of death, no imputation will be implemented for the time afterwards.

6 Sample size

Due to the exploratory nature of the trial, a formal sample size calculation is not applicable [23]. The trial has two subgroup strata (I) sex (male/female); (II) condition of the skin (no IAD vs. IAD Category 1A) and three treatment arms. Based on these conditions and following the recommendations for exploratory trials [36], a sample size of $n = 60$ participants per treatment group is considered feasible and sufficient to describe group differences. In order to compensate a possible loss-to-follow-up, $n = 70$ patients per group will be included.

7 Statistical analyses / methods

For all analyses, appropriate descriptive statistics (mean, standard deviation, median, interquartile range, absolute and relative frequencies) depending on the scale and distribution of the outcome variable for each time point will be presented. For relative frequencies of outcome variables, their cumulative incidences will be reported as well. Sensitivity analyses include per protocol analyses and complete case analyses in the ITT (without imputation).

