7.2 Analyses of endpoints

Because of the exploratory nature of the trial and according to methodological guidance for exploratory trials, a distinction between primary and secondary endpoints is not made [23]. Because the main aim is to prevent IAD, IAD incidence is likely to be considered as a primary outcome in a possible subsequent confirmatory trial and is therefore considered as primary efficacy variable.

For all outcomes, total group differences are reported by the corresponding effect size based on the statistical models as outlines below and corresponding 95% confidence intervals. Relevant timepoints will be Day 6 and Day14. Day0 reports will be presented as is.

The relevant blinded group comparisons are: A vs. B; A vs. C; B vs. C.

For cumulative incidence rates of IAD, Kaplan-Meier Curves will be presented with time ranging from inclusion to IAD onset, i.e. the first occurrence of IAD 2A or 2B. Censoring occurs if patients withdraw from the study before the onset of an IAD or if the study is terminated before IAD onset. Mixed effects Cox regression model (shared frailty model) will be carried out for group comparisons of incidence rates. The latter includes group allocation, sex, setting (nursery home, geriatric hospital ward) and time (continuous) as fixed effects and random intercepts for the ward and the patients. The resulting Hazard ratios for IAD will be presented. Potential non-linear time effects will be explored and modelled using fractional polynomials or splines.

Group differences for categorical, dichotomous responses are calculated by estimating group effects from either generalized linear mixed-effects models (binary logistic) - including particular baseline status (maceration, IAD-related itch), group allocation, sex, setting and time as fixed effects and random intercepts per ward and patients - or nonparametric analysis of longitudinal data depending on the distribution of the data. For the Erosion model, no baseline adjustment is considered due to its presence is an exclusion criterion.

List:

- Erosion (no/ yes)
- Maceration (no/ yes)
- IAD related itch (no/ yes) [only measured if IAD present]
- IAD-related pain (no/yes) [only measured if IAD present]

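### The main Cox model and the erosion model omit Day 0 IAD status (none vs 1A), which randomisation does not balance, so no overall effect estimate is adjusted for it

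*Combined protocol and SAP*

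**What the plan says.** **Sample size.** Protocol 2.8.1 supports 60 per arm with this description: "The trial has two strata (I) sex (male/female); (II) condition of the skin (no IAD vs. IAD Category I) and three study arms". SAP section 6 repeats it in changed words: "The trial has two subgroup strata (I) sex (male/female); (II) condition of the skin (no IAD vs. IAD Category 1A) and three treatment arms".

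**Randomisation.** Protocol 3.1 states that "block-randomization with 1:1:1 allocation ratio per trial arm will be used" and that "the randomization will be stratified according to males and females". Setting enters through separate lists: "Two independent randomization lists are generated according to the same principle", one for hospitals or wards and one for nursing homes. SAP 1.2 names sex alone: "Patients are randomized stratified by sex (male/female) into the treatment arms". Skin condition appears in neither section.

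**Main model.** SAP 7.2 defines the event as first GLOBIAD 2A or 2B. Of the Cox model it says: "The latter includes group allocation, sex, setting (nursery home, geriatric hospital ward) and time (continuous) as fixed effects", plus random intercepts for ward and patient.

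**Erosion model.** "For the Erosion model, no baseline adjustment is considered due to its presence is an exclusion criterion".

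**Baseline status elsewhere.** Protocol 2.2.2 admits both intact skin without IAD and category 1A. Protocol 2.7.1 records the category at Day 0. SAP 7.3 prespecifies baseline 1A status as a subgroup, with treatment interactions and subgroup effects with 95% intervals. It adds a second time-to-event analysis, for IAD of any category, in those without initial IAD.

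**The concern.** The population mixes people with no IAD and people already at the first grade of the scale on which the event is defined. It is plausible that the second group reaches 2A or 2B sooner, although the documents give no figure for this. If the arms differ by chance in their share of 1A, that difference passes into the unadjusted hazard ratio.

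The omission also departs from the SAP's own practice. Maceration, itch, visual erythema and the interval-scaled outcomes are all adjusted for their baseline value; the main outcome is not. The reason given for erosion explains why baseline erosion is not needed as a covariate. It does not bear on 1A versus no IAD, which does vary at Day 0.

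The stated primary objective (protocol 1.2, SAP 1.1.1) is to estimate effect sizes for a later confirmatory trial. The point estimate is therefore the main product, and a chance shift in it carries into the next trial's planning.

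**Working it through.** **1. The plan's own figures.** There is no power calculation to reproduce. The counts agree: 3 × 60 = 180 and 3 × 70 = 210. The two factors in 2.8.1 crossed with three arms give 2 × 2 × 3 = 12 cells, or 180/12 = 15 per cell if evenly filled. Randomisation does not secure that for skin condition.

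**2. Where each factor is used.**

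| Factor | Randomisation | Main Cox model | Erosion model | SAP 7.3 |
|---|---|---|---|---|
| Sex | yes | yes | yes | subgroup |
| Setting | yes (separate lists) | yes | yes | no |
| Day 0 IAD (none vs 1A) | no | no | no | subgroup |

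The example results table for the Cox model (SAP 10.2, Table 2) lists only study arm and sex as predictors.

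**3. Chance imbalance.** The share with 1A is not given. I assume p = 0.354, the long-term-care IAD prevalence in protocol 1.1, with a range of 15-50%; 70 per arm is the planned number.

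- SD of the difference between two arms = √(2 × 0.354 × 0.646 / 70) = 0.081, or 8.1 points. At p = 0.15 it is 6.0 points and at p = 0.50 it is 8.5.
- Simulated binomial draws (400,000): a given pair of arms differs by 10 points or more with probability 25%, and at least one of the three pairs does so with probability 48% (27-52% for p from 15% to 50%).

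**4. Shift in the hazard ratio.** With H the assumed hazard of 1A relative to no IAD and d the imbalance, the spurious ratio is approximately [1 + (H−1)(p + d/2)] / [1 + (H−1)(p − d/2)].

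| H (assumed) | d = 8.1 points (1 SD) |
|---|---|
| 2 | 1.394/1.314 = 1.06 |
| 4 | 2.183/1.941 = 1.12 |
| 6 | 2.972/2.568 = 1.16 |

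With the share varied to 15% and 50% and H still 2 to 6, the 1-SD shift runs from 5% (1.180/1.120 = 1.05) to 19% (1.901/1.599 = 1.19).

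**5. Compared with the sampling error.** I assume 14-day risks of 2A/2B (no IAD vs 1A) and no true effect. Expected events in two arms of 70 = 140 × [risk without IAD + 0.354 × (risk difference)]. The 95% interval runs from the estimate divided by, to the estimate times, exp(1.96 × 2/√events).

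| Assumed risks | Events | Crude HR, 10-point imbalance | Interval factor |
|---|---|---|---|
| 5% vs 10% | 9.5 | 1.08 | 3.57 |
| 5% vs 20% | 14.4 | 1.17 | 2.81 |
| 10% vs 30% | 23.9 | 1.14 | 2.23 |

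**6. Adjusted against unadjusted.** I ran two-arm Cox simulations: 70 per arm, seven follow-up visits, no frailty term, and up to 1,000 trials per scenario (a few with too few events were dropped).

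- True HR 1: mean log HRs agree (−0.014 vs −0.013; 0.001 vs −0.003; 0.013 vs 0.008, unadjusted first).
- SD of log HR is almost unchanged: 0.744 vs 0.746; 0.594 vs 0.592; 0.432 vs 0.438.
- True HR 0.5: −0.758 vs −0.779 (5% vs 20%) and −0.726 vs −0.750 (10% vs 30%), shifts of 0.021 and 0.024.
- Within a single trial the two HRs differ by a factor whose 95th percentile is 1.21 to 1.35 across all five scenarios.

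**The case against.** The strongest reply is that the plan does model this variable. SAP 7.3 gives treatment effects by baseline 1A status, and effects within a status group are not driven by imbalance in that status between arms. A reader might infer that baseline IAD is left uncontrolled throughout; 7.3 rules that out. What remains is that interactions and subgroup effects do not amount to one adjusted overall hazard ratio, and the any-IAD analysis drops the 1A participants and changes the event.

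A reader might also infer that the trial failed to carry out a planned stratified randomisation. The documents do not support this. Protocol 2.8.1 does not say that skin condition is a randomisation stratum, 3.1 states the randomisation factors plainly, and SAP 6 already uses the term subgroup strata. One protocol phrase needs reconciling.

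The sizes rest on assumptions. The 35.4% is prevalence of IAD of any form in long-term care, not the share with 1A among eligible participants, and no hazard for 1A is given. This stands.

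It might be argued that omission costs power or pulls the hazard ratio materially towards 1. The simulations show a shift of only about 0.02 on the log scale and almost no gain in precision, and the plan runs no confirmatory test.

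Nor is a defect shown in the itch and pain models. Itch is adjusted for its own baseline, which is coded not applicable when no IAD is present (SAP 4.2). Numeric pain is also adjusted for baseline, and both outcomes are measured only when IAD is present.

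**Conclusion.** The point holds for two models: the main Cox model and the erosion model should carry Day 0 IAD status and do not. There is no bias on average when the true effect is nil. The exposure is to chance imbalance: about 6-16% in the hazard ratio per SD of imbalance, assuming 35.4% with 1A, 70 per arm and a two- to six-fold hazard. That is smaller than the likely interval, whose limits lie a factor of about 2.2 to 3.6 from the estimate under the assumed event risks. It is still worth removing, because the trial's purpose is to supply an effect size and the variable is already collected. The case rests on chance imbalance and on consistency with the SAP's other models.

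**What to change.** - In SAP 7.2, add Day 0 IAD status (none vs 1A) to the main time-to-event model, as a fixed effect or as a Cox stratum, and to the erosion model as a fixed effect. Keep the SAP 7.3 analyses as they are.
- If group results are already known, report the adjusted models as a labelled sensitivity analysis.
- Reconcile the two-strata statement in protocol 2.8.1 with section 3.1 by calling skin condition a subgroup or analysis factor, in line with SAP 6.

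The cost is one corrected phrase and one extra parameter in each model. With perhaps 10 to 24 events per pair of arms under the assumptions above, that parameter is not entirely free in a Cox model that already has several terms. Using status as a Cox stratum avoids estimating its coefficient. No sample size changes.

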2.8.2 INTERVIEW PART

From the patients included in the trial, $n = 12$ participants (four participants per study arm) will be invited to participate in a qualitative interview. This number is based on the recommendations for doing qualitative research in feasibility studies for RCTs [22]. To identify possible sex-specific differences, two male and two female participants will be interviewed per study arm.

2.9 RECRUITMENT

2.9.1 INSTITUTIONAL LEVEL

Potentially eligible local nursing homes and geriatric hospitals or hospitals with geriatric wards will be contacted and invited to participate by letter, Email or phone. If the institution is interested in the project, an initial in-person meeting is arranged at the facility. Nursing homes and geriatric hospital wards are informed about the aims and scope of the project.

The following advantages or rewards will be offered to the nursing homes in case of participation:

- (1) Certificate of participation if desired (e.g. for marketing purposes of the institution)
- (2) Free in-house education (certificates of attendance for the employees if desired)
- (3) Free educational materials (printed materials including booklets, handouts, posters)
- (4) Free provision of skin cleansing and protection products as well as incontinence materials (including disposable wash mitts, incontinence pants) for participating residents/patients.

2.9.2 PARTICIPANT LEVEL

The recruitment of participants in the geriatric hospitals/wards and the nursing homes will be realized in close cooperation with the local responsible contact person on-site. The responsible contact person can either be the nursing home manager itself or a qualified person, delegated by the management, such as the nursing care manager. The responsible person in the institution will inform possible eligible residents/patients and hand out a first study information leaflet. Interested residents or their legal representatives will then be contacted by the study team in person and will be informed about the conduct of the study.

3. METHODS: ASSIGNMENT OF INTERVENTIONS

3.1 SEQUENCE GENERATION

A computer-generated, block-randomization with 1:1:1 allocation ratio per trial arm will be used. In order to detect any possible sex-related differences or interactions [37] the randomization will be stratified according to males and females. Two independent randomization lists are generated according to the same principle, one for participants in the geriatric hospitals/wards and one for the participants of the nursing homes. This is done to ensure that there is an equal distribution of allocation in both settings. Computerized random numbers will be generated by the statistician not involved in study planning or any further study-related procedures or the associated data analysis. The random number list is kept with the statistician until the end of the study.

3.2 ALLOCATION CONCEALMENT MECHANISM

The allocation will be conducted by the investigator using numbered opaque envelopes (GH-001 to GH-200 for participants in geriatric hospitals/wards; NH-001 to NH-200 for participants in the nursing homes) containing the computer-generated random numbers. The used envelopes are prepared by an employee who is not involved in the planning of the study, the associated data analysis, or any further study-related procedures.

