3.3 BLINDING

Due to the nature of the intervention, involved caregivers and participants will not be blinded. In addition, the person of the study team who reviews the diaries and verifies the correct performance of study-related procedures by nurses is also not blinded. Because the diaries provide information about assignment to the study arm, blinding of the reviewer is not possible due to the given circumstances. In order to enhance the internal validity, every visit will be performed by two members of the study team.

Member 1 of the study team performs the following tasks:

- (I) Conduct of the study visit and its related tasks as listed in Table 3 under the section "Clinical skin assessment" (including assessment of IAD-related pain, itch, patient satisfaction as well as the instrumental measurement of the erythema). Member 1 **does not conduct** any part of the assessment regarding the condition of the skin, which includes GLOBIAD IAD categorization as well as the visual inspection of erythema, erosion and maceration.
- (II) Conduct of monitoring activities as described in Table 1 under the section "11. How well".

Member 2 ("outcome assessor") of the study team is blinded and does the skin condition-related assessments only (including GLOBIAD IAD categorization as well as the visual inspection of erythema, erosion and maceration). The blinded person documents the results of the skin assessment on a separate "Skin Assessment Data Collection Form" (see **Fehler! Verweisquelle konnte nicht gefunden werden.**), independently from the main CRF (see **Fehler! Verweisquelle konnte nicht gefunden werden.**). This procedure is necessary to prevent accidental unblinding of the outcome assessor by trial group-specific information collected in the main CRF. The Skin Assessment Forms will be reintegrated into the main CRF after the respective participant has completed the study or ended its participation.

The data manager will be blinded throughout the period of data entry and verification until data base closure. The trial statistician will be blinded during statistical analysis.

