5.2 ELECTRONIC DATA CAPTURE

Data entry

The CTO uses secuTrial® - a Remote Data Entry (RDE) software solution of interActive Systems (iAS) - to capture trial data and transfer them to a central database. SecuTrial® is in compliance with the regulatory standards (FDA CFR 21 Part 11 and GCP) and contains the required features like audit trail, assigned roles and rights of study employees, management concept and electronic signatures.

The system provides the eCRF which allows the documentation of trial data online at any time by using a standard internet browser (e.g. Chrome, Firefox, Opera, etc.). Furthermore the eCRF contains functions to perform plausibility, consistency and range checks of the entered data to get a high level of data quality. Access to the eCRF is person-specific and password protected. All access rights (read or enter data) will be defined depending on their function in the trial (principle or clinical investigator, study assistant etc.).

The communication between the client-PC and the trial database on the server is based on the secure data-transfer-protocol (SSL - Secure Sockets Layer). This will prevent any illegal access to the trial data by unauthorized parties.

Query Management

There is a Query management tool as an integrated part of the RDE system. This tool allows the communication between the CTO and the clinical investigator at the site. In case of uncertainties, errors or improper data, the CTO or the monitor can set queries to clarify the affected question.

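### Blocked allocation is dispensed from envelopes by the role that also answers for consent, and no varied or withheld block length is described, so past assignments could inform who is enrolled next

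*Combined protocol and SAP*

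**What the plan says.** - **Sequence (protocol 3.1).** "A computer-generated, block-randomization with 1:1:1 allocation ratio per trial arm will be used". Further, "the randomization will be stratified according to males and females", and there is one list per setting: "Two independent randomization lists are generated according to the same principle, one for participants in the geriatric hospitals/wards and one for the participants". This gives four sequences (two settings by two sexes). Block length is not given, and nothing says it varies or is withheld from recruiters.
- **Dispensing (3.2).** "The allocation will be conducted by the investigator using numbered opaque envelopes". The envelopes carry one number series per setting and are prepared by an uninvolved employee. Sealing, consecutive opening, a log and custody are not mentioned, nor is the way the sex strata are drawn from a single series.
- **Custody of the list (3.1).** "The random number list is kept with the statistician until the end of the study"; that statistician takes no part in planning or analysis.
- **Enrolment (2.9.2, 6.3).** "Interested residents or their legal representatives will then be contacted by the study team in person". Information and consent are the investigator's responsibility and may be delegated to the study team.
- **Who knows the arms (3.3, 2.4.2).** Caregivers and participants are unblinded, and "the person of the study team who reviews the diaries and verifies the correct performance of study-related procedures by nurses is also not blinded". A colour-coded card in the room shows the arm. Member 2, who rates GLOBIAD, is blinded.
- **Timing (2.3, Table 3).** Randomisation is on Day 0 after the baseline visit; screening runs from Day -5 to Day 0.
- **Main model (SAP 7.2).** The Cox model for first IAD 2A or 2B has group, sex, setting and time as fixed effects, and ward and patient as random effects.

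**The concern.** In a trial where arms are visible after allocation, concealment has to protect the next assignment as well as the list. Blocking makes the next assignment partly deducible from past ones. Opaque envelopes do not prevent this, because the inference is made before an envelope is opened.

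The role that opens envelopes sees the arms and also answers for consent. Several entry conditions need judgement: whether a person is at the end of life, whether the stay will last 14 days, and whether another skin condition needs treatment (2.2.2). Long-stay residents can also be approached sooner or later. So there is room to choose or time candidates without breaking a rule.

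At stake is the balance of baseline risk. Participants with category 1A at entry already have early IAD. Section 2.8.1 names skin condition as a stratum, but 3.1 does not stratify on it, so the randomisation does not force balance in 1A. Estimating effect sizes for a confirmatory trial is the primary objective (SAP 1.1.1), and a blinded outcome assessor does not correct a difference in who entered each arm.

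**Working it through.** The plan gives no figure for predictability and no block length, so there is nothing to reproduce. Block length is an assumption, shown as a range.

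**Inputs from the documents.** Three arms, 1:1:1 (3.1). Planned total 3 × 70 = 210 (2.8.1). Recruited: 14 + 11 = 25 in acute care and 195 in 18 nursing homes, 220 in all (SAP section 3).

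**Upper bound: constant, known blocks and every earlier assignment in the stratum known.** Let a block have k places per arm (length 3k).

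- *Certain assignments.* An assignment is certain once only one arm is left in the block. For a given arm, the expected number of its places that fall after all 2k places of the other arms is k/(2k+1). Summing over three arms and dividing by 3k gives a share of 1/(2k+1).
- *Best guess.* Name the arm with most places left. For k = 1 the success rate is (1/3 + 1/2 + 1)/3 = 11/18. Larger k needs a recursion over the remaining counts.

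| Block length | Certain | Of 210 | Correct guess |
|---|---|---|---|
| 3 | 1/3 = 33.3% | 70 | 11/18 = 61.1% |
| 6 | 1/5 = 20.0% | 42 | 101/180 = 56.1% |
| 9 | 1/7 = 14.3% | 30 | 4021/7560 = 53.2% |
| 12 | 1/9 = 11.1% | about 23 | 51.2% |

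Chance is 33.3%.

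**Partial knowledge (assumption).** Suppose each earlier assignment in a block of 3 is known with probability 1/2. The success rates by position are 1/3, then 1/2 × 1/2 + 1/2 × 1/3 = 5/12, then 1/4 × 1 + 1/2 × 1/2 + 1/4 × 1/3 = 7/12. Their mean is 4/9 = 44%. By simulation, blocks of 6 and 9 give about 41% to 43%. If a quarter is known, all three lengths give about 38%.

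**Varied, undisclosed lengths.** Guessing the least-used arm so far is right in about 54% of cases for lengths 6/9 and about 53% for 6/9/12 (simulation, one sequence of 195, all past assignments known). No block boundary is known, so certainty goes, but guessing stays well above chance.

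**Route to the result.** SAP 7.2 adjusts most of the secondary models for baseline status but not the Cox model. A 1A imbalance would therefore pass into the main hazard ratios.

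**Illustration only.** Assume 35.4% of candidates have 1A (the IAD prevalence in protocol 1.1, borrowed), a choice between two candidates each time, blocks of 6, and 2A/2B risks of 20% with 1A and 5% without. In simulation, acting on the guess half of the time gives 30% 1A in control against 39% in the product arms; always acting gives 23% against 42%. With no true effect the bias is (0.39 − 0.30) × 0.15 = 1.4 points, or (0.42 − 0.23) × 0.15 = 2.8 to 2.9 points. A variant with random tie-breaking gives 1.2 to 2.3. For scale, the overall risk is 0.354 × 0.20 + 0.646 × 0.05 = 0.103, and the 95% half-width for a two-arm difference is 1.96 × √(2 × 0.103 × 0.897/70) ≈ 10 points.

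**The case against.** The strongest reply is that the documents do not show predictability; they leave safeguards undescribed. Block length is often kept out of a protocol that recruiters can read, so silence does not mean constant blocks. An uninvolved statistician keeps the list, an uninvolved employee prepares the envelopes, and allocation follows the baseline visit. Ascending participant numbers (6.5) point to use in order, although envelopes are not expressly tied to them. This stands as far as it goes: the percentages are conditional. It does not answer the lack of separation between enrolment and dispensing, which is stated.

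Three stronger readings are tempting, and the documents do not support them.

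- *That the whole study team knows every assignment.* Member 2 is blinded, section 4.1 speaks of several trained assessors, and no section says that one person sees all diaries across 18 homes. Home staff see only their own share of a list that spans all homes.
- *That the distinction between no IAD and category 1A is an entry judgement open to steering.* Both are eligible (2.2.2), and the GLOBIAD rating belongs to the blinded assessor. The possible route is choice and timing of candidates, not miscategorised skin.
- *That the trial is biased by some percentage points.* The illustration stacks full knowledge, constant blocks, interchangeable candidates and assumed risks.

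The SAP also mitigates part of the consequence. Day 0 IAD status will be reported (4.2, 7.2). Section 7.3 plans effects by baseline 1A status and a second time-to-event analysis in those without initial IAD, and an imbalance in 1A would not confound these. The main hazard ratios remain exposed.

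**Conclusion.** The point holds as a weakness in the allocation method, not as evidence that anyone steered enrolment. Dispensing sits with the role responsible for consent, in a blocked and open setting, and no varied or withheld block length is described. The safeguards that exist stop the list from being read but not inferred.

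The size is an upper bound of 53% to 61% correct guesses for blocks of 9 to 3, with 14% to 33% of assignments certain. It rests on constant known blocks and full knowledge within a stratum. With half of the history known, guessing falls to about 41% to 44%. The link to the result is firmer: as the model is written, any 1A imbalance, however it arose, reaches the main hazard ratios unadjusted. The bias illustration, about 1 to 3 points for blocks of 6 against a half-width of about 10, shows only what is possible under its assumptions.

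**What to change.** **For the method (3.1 and 3.2), now of use to the confirmatory trial.**

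- Replace envelopes dispensed by the investigator with release of each allocation through the existing secuTrial eCRF (described in 5.2 as a "Remote Data Entry (RDE) software solution"), or by the CTO or the list-holder on request. Release should come only after consent, eligibility and the Day 0 skin assessment are recorded.
- State that block lengths vary at random and are known only to the list-holding statistician. This removes certain assignments but leaves guessing near 53%, so it supplements external release and does not replace it.

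The cost is a regenerated list, set-up in a system the CTO already runs, a connection or call at each allocation, and slightly looser balance within strata. No extra participants or assessors are needed.

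**For this trial, with recruitment complete (SAP section 3).**

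- Report the block scheme, the envelope log (including how the sex strata were drawn) and who judged eligibility.
- Tabulate Day 0 IAD status by arm and by position within block.
- Optionally, add a sensitivity Cox model with Day 0 IAD status as a covariate.

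These steps use data and records that should already exist and cost little more than reporting effort.
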